In this respect, cetuximab appears to have a different toxicity profile than that of traditional chemotherapy such as cisplatin. The most commonly reported side effect is the development of skin reactions including macular, papular, and pustular rashes, xerosis, fissures, telangiectasias, and hyperpigmentation of the hair and nails (Bernier et al., 2008). The most frequent of these reactions is an acne-like rash that predominately appears in areas rich in sebaceous glands. The acne-like rash comprises itchy erythematous follicular papules that evolve into pustules. Other presentations include diffuse erythema with follicular papulopustules and telangiectasia, a seborrhoeic dermatitis-like rash or, occasionally, an edematous facial erythema. In the absence of radiation, the acne-like rash can be seen within a few days of the initiation of treatment and peaks 2–3 weeks after starting therapy (Bernier et al., 2008).

The effect on the skin during the combination of cetuximab and radiation is of considerable interest, as it might require special care to reduce symptoms and severity. It appears that radiation may delay the onset of the cetuximab-induced rash as it typically appears within irradiated fields 3–5 weeks after initiation of treatment (Bernier et al., 2008). There appears to be no obvious relationship between the severity of cetuximab-associated acne-like rash outside irradiated fields and the severity of radiation dermatitis. The aforementioned Phase III trial (Bonner JA et al., 2010) revealed no statistically significantly increase in the incidence or severity of radiation dermatitis compared with radiotherapy alone. The incidence of grade 3 radiation dermatitis was 18% with RT alone and 23% with RT with cetuximab ($p = 0.27$). There was a slight increase in the median duration of radiation dermatitis in the cetuximab arm (11.1 weeks) compared with the RT-alone arm (9.4 weeks).

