process. Its clinical utility in reducing oral mucositis was assessed prospectively and was recently discussed in a Cochrane review (Clarkson et al., 2010; Guatuum AP et al., 2012; Migliorati et al., 2013). Here, LLLT showed a reduction in severe mucositis when compared with the sham procedure (risk ratio: 5.28, 95% confidence interval: 2.30 to 12.13). While these studies support an improvement in oral mucositis with LLLT, the clinical experience addressing an improvement in cetuximab-induced rashes and radiation-dermatitis is limited. An Italian case series (Gobbo et al., 2011) reported that in 4 patients with metastatic colorectal cancer and two patients with HNSCC, LLLT reduced cetuximab-related skin toxicities. Here, patients were treated with two 8-minute long consecutive sessions/day over a 4-day treatment. Patients were evaluated weekly for up to 3 weeks and after 180 days. Follow-up evaluations including a questionnaire about the onset and progression of the acneiform rash and visual analog scales were reported. The authors reported that after the fourth session of LLLT, the patients showed a decrease in both cetuximab-related toxicity and visual analog scales, up to complete regression of the lesions in all treated areas (Gobbo et al., 2011). No adverse effects from treatment were reported. These findings suggest that LLLT may be an effective way of managing cetuximab- and radiation-induced skin toxicities. Herein we propose a pilot study to assess the efficacy of LLLT to mitigate and ameliorate the acneiform-rash, radiation dermatitis, and pain while assessing its impact on PR-QoL measures.

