6.0 Procedures Involved

6.1 Screening / Pre-treatment:

- Medical history
- Physical examination, including Karnofsky Performance Status and vital signs.
- Signed informed consent
- Subject body weight and height
- Quality of Life Assessments (UW QoL, BPI, DLQI)

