6.2 Evaluation during Treatment

- Patients will be treated with the 69 diode LED cluster probe. The wavelength utilized are both 660 nm and 850 nm. The average power density is 100 mW/cm² and the spot size is 0.2 cm². Treatment time is 60 seconds to each site. There are a minimum of nine treatment sites: (1) left forehead, (2) right forehead, (3) left upper cheek/malar region, (4) right upper cheek/malar region, (5) right lower cheek / trigeminal nerve mandibular division distribution, (6) left lower cheek / trigeminal nerve mandibular division distribution, (7) submental region, (8) left neck, (9) right neck. Patients will be pretreated with a minimum of 3 sessions over 7 days before starting radiotherapy. Patients will receive LLLT at least twice the week prior to initiation of radiation and then at least three times per week during the course of radiation treatment.

- Adverse Event Assessment (Grading of skin toxicity and mucositis by patient)
- Completion of patient reported DLQI during treatment week 5 and at end of treatment

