6.3 Evaluation following Treatment

- Patients will be seen in follow-up at least every three months in the first year following completion of treatment.
 - Observer reported mucositis and skin reaction every three months for one year
 - Patient reported QoL assessments (UQ QoL, BPI, DLQI) every three months for one year

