14.2.2 Analysis of Secondary Endpoints

University of Washington Quality of Life questionnaire (UW-QOL): The UW-QOL consists of 12 single question domains focusing on current patient health and quality of life within the past 7 days. These domains have between 3 and 6 response options that are scaled evenly from 0 (worst) to 100 (best) according to the hierarchy of response. The domains are pain, appearance, activity, recreation, swallowing, chewing, speech, shoulder, taste, saliva, mood and anxiety; patient choice of up to three of these domains that have been the most important to them. There are also three global questions, one about how the patient feel relative to before they developed their cancer, one about their health-related QOL and one about their overall QOL. In regard to their overall QOL, patients are asked to consider not only physical & mental health, but also many other factors, such as family, friends, spirituality or personal leisure activities that were important to their enjoyment of life.

Brief Pain Inventory (BPI): The BPI allows patients to rate the severity of their pain and the degree to which their pain interferes with common dimensions of feeling and function.

Dermatology Life Quality Index (DLQI): The DLQI is a ten-question questionnaire designed to measure the health-related quality of life of adult patients suffering from a skin disease. Each question is scored from 0 to 3, giving a possible score range from 0 (meaning no impact of skin disease on quality of life) to 30 (meaning maximum impact on quality of life).

For all these QoL measures, descriptive statistics (mean, SD, median, and inter-quartile range) will be primarily used to summarize the scored scales at each scheduled assessment time point. Additionally, change from baseline in the domain scores at the time of each assessment will be summarized. Patients with an evaluable baseline score and at least one evaluable post baseline score during the treatment period will be included in the change from baseline analyses. Mixed effect model for repeated measures (MMRM) will be used to examine the change of QoL measures with time and treatment.

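### Pain (BPI) and head-and-neck QoL (UW-QOL) have no scheduled assessment during laser treatment or at its end, and the change-from-baseline rule in 14.2.2 needs one.

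*Combined protocol and SAP*

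**What the plan says.** Section 3.2 describes a pilot study of whether the laser can "mitigate and ameliorate the acneiform-rash, radiation dermatitis, and pain while assessing its impact on PR-QoL measures". Section 4.2 makes the UW-QOL, BPI and DLQI the three secondary endpoints. Under section 6.2 the laser starts in the week before radiotherapy and continues through the course; none is scheduled afterwards.

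The three instruments are scheduled as follows:

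- **Screening (6.1):** UW-QOL, BPI and DLQI.
- **During treatment (6.2):** "Completion of patient reported DLQI during treatment week 5 and at end of treatment". The only other patient-reported item here is the patient's own grading of skin toxicity and mucositis.
- **After treatment (6.3):** "Patient reported QoL assessments (UQ QoL, BPI, DLQI) every three months for one year". I read the first abbreviation as a misprint for UW-QOL. The visit rule is "Patients will be seen in follow-up at least every three months in the first year following completion of treatment".

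Section 14.2.2 describes the UW-QOL as "focusing on current patient health and quality of life within the past 7 days". For all the QoL measures it plans summaries at each scheduled time point, change-from-baseline summaries and a mixed model for repeated measures. A patient enters the change-from-baseline analyses only with a usable baseline score and at least one usable later score from the treatment period.

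**The concern.** The laser is given before and during radiotherapy, so its effect on pain and QoL would be looked for first in those weeks. Pain severity and interference are assigned to the BPI. Swallowing, chewing, speech, taste and saliva are among the UW-QOL domains. Neither form is scheduled in those weeks. The DLQI covers skin-related QoL then, but it does not replace the other two.

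Two things are at stake. First, two of the three secondary endpoints hold no information on the period of the intervention, and scores not collected then cannot be recovered later. Section 12.1 also plans to set the patient-reported endpoints beside historical reports; for these two instruments only late values would be available. Second, the inclusion rule in 14.2.2 asks for a score that the schedule never collects. Read literally, it removes every patient from the BPI and UW-QOL change-from-baseline analyses, including change to months 3 to 12.

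**Working it through.** The plan gives no figure of its own on this point. The check is a count of scheduled forms, a comparison with the analysis rule, and some calendar arithmetic as illustration.

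**1. Scheduled forms per patient (6.1, 6.2, 6.3).** Follow-up forms number 12 months / 3 months = 4.

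| Instrument | Screening | Week 5 and end of treatment | Follow-up | Total |
|---|---|---|---|---|
| DLQI | 1 | 2 | 4 | 7 |
| BPI | 1 | 0 | 4 | 5 |
| UW-QOL | 1 | 0 | 4 | 5 |

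No other section schedules the BPI or UW-QOL.

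**2. Against the inclusion rule in 14.2.2.** The rule needs at least one score after baseline and within the treatment period. I take that period to be the laser and radiotherapy course, since 6.3 places its forms after completion of treatment. Scheduled scores that meet the rule are 2 for the DLQI, 0 for the BPI and 0 for the UW-QOL. Patients who can qualify through the schedule on the BPI or UW-QOL: 0 of 75.

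**3. Length of the gap.** Three months is (365.25 / 12) × 3 / 7 = 13.0 weeks. The documents do not give the length of radiotherapy; I assume 6 to 7 weeks.

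- From the start of radiotherapy to the first later BPI or UW-QOL: 6 + 13 = 19 to 7 + 13 = 20 weeks.
- From baseline, with the one-week laser lead-in: 1 + 19 = 20 to 1 + 20 = 21 weeks.

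A 7-day look-back at week 19 or 20 reaches back only to week 18 or 19, about 12 weeks after radiotherapy ends.

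**4. Illustration: where the skin reaction falls in that gap.** Section 3.1 gives median durations of radiation dermatitis of 9.4 weeks (radiotherapy alone) and 11.1 weeks (with cetuximab). Onset is not given; I assume anywhere from week 2 to the last week of radiotherapy.

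- Median resolution = onset + duration: earliest 2 + 9.4 = week 11.4; latest 7 + 11.1 = week 18.1.
- Gap from resolution to first form: longest 20 − 11.4 = 8.6 weeks; shortest 20 − 18.1 = 1.9 weeks (the same for a 6-week course: 19 − 17.1 = 1.9).
- If durations were exponential, the share of affected patients still affected at the first form is 0.5^((form − onset) / median): from 0.5^(18 / 9.4) = 0.27 to 0.5^(13 / 11.1) = 0.44.

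The study summary describes a population on chemotherapy with concurrent radiotherapy, so the radiotherapy-alone median may fit poorly. With 11.1 weeks only, the gap is 1.9 to 20 − 2 − 11.1 = 6.9 weeks, and the share is 0.5^(18 / 11.1) = 0.32 to 0.44.

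Steps 1 and 2 need no assumption about radiotherapy length, onset or duration. Step 4 depends on all three.

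**5. After the fix.** The BPI and UW-QOL would each have 2 forms on treatment and 1 + 2 + 4 = 7 in all, and patients who complete them could meet the 14.2.2 rule.

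**The case against.** The strongest reply is that the plan puts the skin-specific instrument where it matters. The DLQI is completed in week 5 and at the end of treatment, patients grade their own skin toxicity and mucositis, and section 10.2 has physicians record toxicities weekly. The hypothesis in section 2.2 concerns grade III dermatitis, and section 4.2 promises only that QoL metrics will be collected. Pain as an aim rests on one sentence in the background. Late pain and QoL are legitimate outcomes in a descriptive study, and 6.3 allows follow-up more often than every three months.

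Much of this stands. Skin-related QoL in the acute phase is covered, and the later visits have value. It does not close the gap. Earlier follow-up visits are allowed but not required, the questionnaire item itself is three-monthly, and any such visit would still come after treatment. Toxicity grades are not BPI or UW-QOL scores. The 14.2.2 rule covers all the QoL measures, which suggests that on-treatment scores were expected for each.

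A reader might go further and infer four things that the documents do not support:

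- **That month-3 BPI would be near baseline whether or not the laser works.** The documents give no BPI values and no pain trajectory, and pain can have other causes, such as mucositis.
- **That month-3 scores would be presented as the course of pain under the laser.** Section 14.2.2 summarises scores by time point, so they would be labelled as month 3.
- **That the mixed model would draw a line from screening to month 3.** Section 14.2.2 does not say whether time is continuous or categorical; with categorical visits nothing is interpolated.
- **That adding the forms would show a laser effect on pain.** The trial has one arm and plans no hypothesis test, and section 10.2 expects significant mucositis, so BPI scores would mix skin and mucosal pain.

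**Conclusion.** The concern holds as a gap in the schedule and a conflict between sections 6.2 and 14.2.2. The BPI and UW-QOL have 0 scheduled assessments during the laser course or at end of treatment, against 2 for the DLQI, and their change-from-baseline set is empty as scheduled (0 of 75). The only reading this relies on is that the treatment period excludes the follow-up visits in 6.3. The trial therefore cannot describe pain or head-and-neck QoL during the acute reaction; it can still describe recovery at 3 to 12 months.

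The timing of resolution (1.9 to 8.6 weeks before the first later form) and the 27% to 44% still affected are illustrations under an assumed radiotherapy length, onset and exponential durations. The conclusion does not depend on them. The primary endpoint and the precision statement for 75 patients are unaffected. This should be changed because the repair is cheap and the missing scores cannot be collected afterwards.

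**What to change.** - **Section 6.2:** extend the questionnaire item so that the UW-QOL and BPI are completed together with the DLQI, in treatment week 5 and at end of treatment.
- **Section 14.2.2:** for the BPI and UW-QOL, summarise change from screening to week 5 and from screening to end of treatment. Report months 3 to 12 separately as late recovery. State that the late summary does not require an on-treatment score; otherwise patients treated before the amendment stay excluded from it.

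The first change also reconciles 6.2 with the inclusion rule.

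The cost is a protocol amendment and slightly more patient burden: 2 instruments × 2 time points = 4 more questionnaires per patient, at time points where the DLQI is already completed. No extra visits or patients are needed. Patients already past those time points cannot supply on-treatment scores, and about 13 weeks between end of treatment and month 3 would remain unobserved. The added scores should be reported as descriptive.

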6.3 Evaluation following Treatment

- Patients will be seen in follow-up at least every three months in the first year following completion of treatment.
 - Observer reported mucositis and skin reaction every three months for one year
 - Patient reported QoL assessments (UQ QoL, BPI, DLQI) every three months for one year

7.0 Study Timelines

- The expected duration of an individual subject's participation is approximately 15 months.

8.0 Inclusion and Exclusion Criteria

8.1 Inclusion Criteria:

- Male or female patients \geq 18 years of age
- Karnofsky performance status > 70
- Histologic proof of squamous cell carcinoma of the oral cavity, oropharynx, hypopharynx, or larynx
- No prior radiotherapy to the head and neck region.
- No previous systemic chemotherapy or targeted therapy
- Must be aware of the neoplastic nature of his/her disease and willingly provide written, informed consent after being informed of the procedure to be followed, the nature of the therapy, alternatives, potential benefits, side-effects, risks and discomforts.
- Patients using standard therapies for cetuximab-induced acne-form rash will be included.

8.2 Exclusion Criteria:

- Evidence of distant metastasis on upright chest x-ray (CXR), computed tomography (CT) or other staging studies
- Any co-morbidity or condition of sufficient severity to limit full compliance with the protocol per assessment by the investigator
- Concurrent serious infection
- Continued use of Niacin

9.0 Withdrawal of Subjects

9.1 Patients are to discontinue therapy in the event of:

- Disease progression
- Development of a serious medical illness
- Evidence of dose-limiting toxicity
- Major protocol violation
- Discretion of the principal investigator

9.2 Patients may withdraw from study participation voluntarily.

10.0 Risks to Subjects

10.1 There are few risks associated with low-level laser therapy. This treatment is non-invasive and uses a cold laser output. Infrequently, eye damage has occurred with prolonged visual contact with the laser. Further, patients using concomitant supplemental niacin may experience, facial flushing.

10.2 Although no reported grade 3 or greater toxicities for LLLT have been published, patients will be closely monitored by a certified nurse prior to each delivery. Patients will be instructed to seek alternatives to niacin if taking this medication at the time of enrollment to the study. Additionally, eye protection is provided to all patients and staff present in the examination room during delivery of LLLT to prevent any eye damage. Significant mucositis from radiation is expected. Appropriate supportive care will be provided including analgesia, local therapies, and potentially low level laser therapy. Patients will be monitored weekly by the treating physicians to appropriately manage and record potential toxicities. Patients developing dermatologic adverse events will be monitored for the development of inflammatory or infectious sequelae. Supportive therapies other than the investigational intervention may include the following:

- Antibiotics: The benefit of routine antibiotics in uncomplicated (uninfected) rash is unclear. Some clinicians have used oral minocycline (Minocin), mupirocin (Bactroban), or topical clindamycin (Cleocin). Rash complicated by cellulitis should be treated with appropriate antibiotics based on clinical judgment or microbial sensitivity analysis.
- Antihistamines: Benadryl or Atarax may be helpful to control itching.
- Topical Steroids: The benefit of topical steroids is unclear.
- Retinoids: No data to support use. Use is not advised.

- Benzoyl peroxide: Should NOT be used--may aggravate rash.
- Makeup: Rash can be covered with makeup; this should not make it worse (use a dermatologist-approved cover-up, e.g., Dermablend, or any other type of foundation). Remove makeup with a skin-friendly liquid cleanser, e.g., Neutrogena, Dove, or Ivory
- Skin Cleansing Liqui-Gel.
- Moisturizers: Use emollients to prevent and alleviate the skin dryness, e.g., Neutrogena Norwegian Formula Hand Cream or Vaseline Intensive Care Advanced Healing Lotion.
- Sunlight: It is recommended that patients wear sunscreen and hats and limit sun exposure during treatment as sunlight can exacerbate any skin reactions that may occur.
- Over-the-counter medications: Over-the-counter acne vulgaris medications (e.g., benzoyl peroxide) are not advised. This rash is not like acne vulgaris and these treatments could make it worse.

11.0 Potential Benefits to Subjects

11.1 Taking part in this study may or may not make the subject's health better. While doctors hope that this study treatment will be more useful against cancer compared to the usual treatment, there is no proof of this yet. We do know that the information from this study will help doctors learn more about this drug as a treatment for cancer. This information could help future cancer patients.

12.0 Data Management

12.1 This prospective observational study seeks to describe the toxicities of patients undergoing this intervention. Rates of Grade 3 CTCAE toxicities will be documented, along with PR-QOL secondary endpoints, and will be compared to historical reports of toxicity in the literature.

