1.0 Study Summary

Study Title	Utilization of Low Level Laser Therapy (LLLT) for Radiation-Induced Dermatitis in Patients with Head and Neck Squamous Cell Carcinoma (HNSCC)
Study Design	Single-arm, Phase I/II
Primary Objective/Endpoint	
Assess the safety and efficacy of low level laser therapy (LLLT) in mitigating radiation-induced dermatitis in patients undergoing radiation therapy for head and neck squamous cell carcinoma (HNSCC)
 
Endpoint: Documented Grade 3 or higher Adverse Events as per CTCAE v4.0

Secondary Objective(s)/Endpoints	
assessment of patient-reported quality of life data, pain parameters and dermatologic quality of life responses
 
Endpoints:
 
 • quality of life data measured using the University of Washington Quality of Life Questionnaire (UW-QOL) • pain parameters assessed using Brief Pain Inventory (BPI) • dermatologic quality of life responses measured using the Dermatology Life Quality Index (DLQI)
Research Intervention(s)/Investigational Agent(s)	THOR Laser system
IND/IDE #	N/A
Study Population	patients with histologically proven squamous cell carcinoma of the oral cavity, oropharynx, hypopharynx or larynx who are candidates for either definitive or adjuvant therapy consisting of a chemotherapy regimen and concurrent radiation therap
Sample Size	75 planned
Study Duration for individual participants	15 months

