2.0 Objectives

- 2.1 The study aims to assess the safety and efficacy of the utilization of low level laser therapy to mitigate radiation-induced dermatitis in patients undergoing definitive or adjuvant radiation therapy with head and neck squamous cell carcinoma.
- 2.2 The hypothesis is that low level laser therapy given prior to and during the course of treatment will decrease the rate of grade III dermatitis, a common finding seen in patients undergoing radiation therapy with head and neck squamous cell carcinoma. An additional goal of low level laser therapy is to increase wound healing.

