4.0 Study Endpoints

- 4.1 Primary Endpoint: The primary endpoint is to characterize the rate of any Grade 3 or higher Adverse Events as per CTCAE v4.0 (Common Terminology Criteria for Adverse Events).
- 4.2 Secondary Endpoints: Several patient reported QOL metrics will be collected as secondary endpoints.
 - quality of life data measured using the University of Washington Quality of Life Questionnaire (UW-QOL)
 - pain parameters assessed using Brief Pain Inventory (BPI)
 - dermatologic quality of life responses measured using the Dermatology Life Quality Index (DLQI)

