14.3. Sample Size/Accrual Rate

As stated in Section 14.2, the main goal of this descriptive study is not for hypothesis testing. We plan to accrue 75 patients. With this sample size, the exact 95% CI for the grade 3 AE has a maximum width of 24%. For example, if the observed rate is 15/75 (20%), then the 95% CI will be (12%, 31%). The following is a table for the CI.

Observed proportion of grade 3 AE	Exact 95% CI for the grade 3 AE rate
5/75 (7%)	(2%, 15%)
10/75 (13%)	(7%, 23%)
15/75 (20%)	(12%, 31%)
20/75 (27%)	(17%, 38%)
25/75 (33%)	(23%, 45%)
30/75 (40%)	(29%, 52%)

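### The hypothesis is about grade 3 dermatitis, but the only rate given a confidence interval is any Grade 3 or higher AE, and the historical comparison in 12.1 names neither rate nor benchmark

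*Combined protocol and SAP*

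**What the plan says.** - **Hypothesis (2.2).** The laser "will decrease the rate of grade III dermatitis".
- **Primary endpoint (4.1).** The aim is to "characterize the rate of any Grade 3 or higher Adverse Events as per CTCAE v4.0". It is not limited to skin events.
- **Historical comparison (12.1).** Grade 3 CTCAE toxicity rates, along with the patient-reported endpoints, "will be compared to historical reports of toxicity in the literature". No report, event type, regimen, method or reading rule is named.
- **Analysis (14.2.1, 14.3).** The primary analysis is a frequency, a percentage and an exact 95% CI, not split by regimen. Maximum grade is also recorded for each toxicity type. Section 14.3 states that "the main goal of this descriptive study is not for hypothesis testing". Its precision table is headed "Observed proportion of grade 3 AE", whereas 4.1 counts Grade 3 or higher.
- **Historical figures (3.1).** "The incidence of grade 3 radiation dermatitis was 18% with RT alone and 23% with RT with cetuximab". The cited randomised trial enrolled patients with locally advanced, non-operative disease.
- **Population (1.0).** Patients are "candidates for either definitive or adjuvant therapy consisting of a chemotherapy regimen" with concurrent radiation. The regimen is left open.

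**The concern.** The stated aim includes efficacy, and without a control arm a lower dermatitis rate can be judged only against an external figure. Section 12.1 is the only place that offers such a comparison, and it has no counterpart in the statistical section.

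The headline number and the quoted historical numbers also measure different things. One counts every Grade 3 or higher event in a mixed population; the others count one skin event under two specific regimens. Section 10.2 expects significant mucositis from radiation. Severe mucositis would raise the any-AE rate but has no place in a dermatitis benchmark.

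At stake is whether the trial's main estimate can say anything about 2.2, and whether the comparator is chosen before or after the data are seen.

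**Working it through.** **Step 1. The plan's own precision figures.** Clopper-Pearson 95% limits for x of 75 are the beta quantiles B(0.025; x, 76−x) and B(0.975; x+1, 75−x).

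| x/75 | Plan (14.3) | Recomputed |
|---|---|---|
| 5 | 2%, 15% | 2.2%, 14.9% |
| 10 | 7%, 23% | 6.6%, 23.2% |
| 15 | 12%, 31% | 11.7%, 30.8% |
| 20 | 17%, 38% | 17.1%, 38.1% |
| 25 | 23%, 45% | 22.9%, 45.2% |
| 30 | 29%, 52% | 28.8%, 52.0% |

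The maximum width is 23.6% (at x = 38), against 24% stated. The sample-size section is sound.

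**Step 2. What happens if the pooled rate is set against a dermatitis rate.** Let d be the dermatitis rate and q the rate of other Grade 3 or higher events. The documents give no q, so 10% to 30% is assumed, independent of dermatitis. Then

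any-AE rate = 1 − (1−d)(1−q).

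For d = 18% and q = 20%: 1 − 0.82 × 0.80 = 34.4%. With 75 patients the interval lies above 18% when x ≥ 21 and below it when x ≤ 6. For 23% the counts are x ≥ 26 and x ≤ 9. Binomial probabilities follow.

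*No laser effect: chance that the any-AE interval lies above the dermatitis benchmark*

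| q | any-AE rate, d = 18% | P(above 18%) | any-AE rate, d = 23% | P(above 23%) |
|---|---|---|---|---|
| 10% | 26.2% | 0.40 | 30.7% | 0.26 |
| 20% | 34.4% | 0.90 | 38.4% | 0.78 |
| 30% | 42.6% | 0.997 | 46.1% | 0.98 |

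*Laser halves dermatitis: chance that the interval lies below the benchmark*

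| Rate analysed | 18% → 9% | 23% → 11.5% |
|---|---|---|
| Dermatitis only (q = 0) | 0.48 | 0.64 |
| Any AE, q = 10% | 0.01 | 0.04 |
| Any AE, q = 20% or more | about 0 | about 0 |

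**Step 3. Choice between the plan's own two dermatitis rates.** Here x is a dermatitis count and all 75 patients face one benchmark.

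| x of 75 | Against 18% | Against 23% |
|---|---|---|
| 0–6 | below | below |
| 7–9 | not excluded | below |
| 10–20 | not excluded | not excluded |
| 21–25 | above | not excluded |
| 26 or more | above | above |

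The reading differs at 7–9 and 21–25 only.

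**Step 4. Splitting by regimen.** If the 75 were split 38/37, the interval would lie below 18% only at 2 or fewer events of 38 or 1 or fewer of 37, and below 23% only at 3 or fewer in either group. The counts in Step 3 therefore do not carry over to regimen groups.

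**The case against.** The best defence has three parts.

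**The mismatch is not forced.** Section 12.1 speaks of toxicities in the plural, and 14.2.1 tabulates the maximum grade of each type. A dermatitis rate can be extracted and set against a dermatitis figure. This stands, and it limits the point: Step 2 describes what would follow from one reading of 12.1, not something the plan commits to. But no text says which rate is to be compared, or with what.

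**The study is declared descriptive.** This also stands: no formal type I error is at stake. It does not remove the comparison promised in 12.1 or the directional hypothesis in 2.2.

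**The two benchmarks seldom disagree.** A reader might infer that an open benchmark lets the sponsor reach either conclusion. The documents do not support that. No count out of 75 puts the interval below 23% and above 18%. At 7–9 and 21–25 events the two rates differ only between excluding and not excluding. Wider swings would need literature rates that the documents do not contain.

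A second tempting inference is that 18% can serve for every patient not on cetuximab, so that a benchmark weighted by regimen mix could be built. Section 3.1 gives 18% for RT alone, while the summary in 1.0 describes patients on chemotherapy with concurrent radiation. The documents hold no rate for other chemotherapy regimens, so such a weighted figure cannot be calculated.

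**Conclusion.** The point holds. The only estimate with a planned interval does not address the hypothesis in 2.2, and the one comparison that could address it is unspecified in 12.1 and absent from section 14.

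If the pooled any-AE rate were compared with 18%, an ineffective laser would look worse than history with probability 0.90 at q = 20% (0.40 at 10%, 0.997 at 30%), and a laser that halved dermatitis would almost never look better. These figures rest on the assumed q and on independence. At d = 18% and q = 20%, complete overlap of the two kinds of event would give an any-AE rate of 20%, and no overlap 38%, against 34.4% under independence. With much overlap the false signal of harm would be weaker, but a halving of dermatitis would still be hidden: with full overlap the any-AE rate stays at 20%.

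Choosing between the plan's own two dermatitis rates is a smaller matter, confined to 7–9 and 21–25 events. The exact-interval calculations in 14.3 are not in question. The sponsor should act on this; it does not invalidate the safety description.

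**What to change.** 1. In 14.2.1, add the Grade 3 or higher radiation dermatitis rate with exact 95% CI, overall and by systemic regimen, as the estimate that addresses 2.2.
2. Name the benchmark before analysis, in section 14 as well as 12.1: 23% for RT with cetuximab, and 18% only for any patients given RT alone. Section 3.1 gives both as grade 3, so check the grade definition in the source.
3. Report other chemotherapy regimens descriptively unless a source is named beforehand. Note that the cited trial was in non-operative patients, so the documents hold no benchmark for adjuvant patients.
4. State that the pooled any-AE rate will not be compared with a dermatitis rate.
5. Use Grade 3 or higher throughout, including 12.1 and the table in 14.3.
6. Do not use a benchmark weighted by regimen mix, and do not write in fixed event cut-offs of 6 or 9. Those counts apply only if all 75 patients face one benchmark.

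Alternatively, delete the historical comparison from 12.1 and make no efficacy statement.

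The cost is some wording and one extra table. Intervals by regimen will be wide, and the sponsor has less freedom to choose a comparator later. No extra patients or visits are needed.
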